7.4.3. Analysis of the primary efficacy endpoint and key secondary efficacy endpoints

Label of estimand	Description of estimand	Main estimator			Sensitivity/ Supplementary analysis
		Analysis sets	Rules for imputation	Model/method for the main analytical methods	
Estimand of primary endpoint	
The difference in efficacy in patients aged 12 years and older with moderate to severe AD and weighing > 40 kg between the CBP-201 300 mg Q2W group and placebo group.
 
A patient is considered as treatment success if the patient has an IGA score of 0-1 which is decreased by ≥ 2 points from baseline at W16.
 
A patient should be regarded as treatment failure if he/she uses prohibited drugs/treatments specified in the protocol for which the study treatment must be early terminated or other rescue therapy that has a major impact on the assessment of the primary endpoint due to poor response, or has premature discontinuation of treatment/EOT due to AEs.
	FAS1 (will include all subjects in RS1 who have received the study drug at least once).	
For subjects who experience intercurrent events, their visits after the intercurrent events will be handled in accordance with the strategies for managing intercurrent events listed in Table 7.4.2.
 
If the target variable is still missing after application of the strategies for managing intercurrent events, the multiple imputation (MI) method will be used to impute the missing data in the placebo group, and the J2R (jump to reference) method will be used to impute the missing data in the CBP- 201 group.
	
Differences in response rates between the treatment group and placebo group and their 95% confidence intervals will be analyzed using the Cochran-Mantel-Haenszel test stratified by baseline disease severity (IGA 3 or 4). The Type I error level for statistical significance of the difference in response rates between CBP-201 and placebo is set at 0.05 (two-sided test).
	
Sensitivity analysis 1: When the target variable is still missing after application of the strategy for managing intercurrent events, it will be classified as treatment failure.
 
Sensitivity analysis 2: When the target variable is still missing after application of the strategy for managing intercurrent events, tipping point analysis will be used for analysis.
 
Sensitivity analysis 3: For the subjects who are incorrectly stratified and randomized, the analysis will be performed using the stratification during randomization and the same method as the main estimand;
 
Supplementary analysis 1: The analysis will be performed using the same method as the main estimand based on the PPS1.
 
Supplementary analysis 2: The treatment policy strategy will be used for all intercurrent events; the FAS1 will be used,


Label of estimand	Description of estimand	Main estimator			Sensitivity/ Supplementary analysis
		Analysis sets	Rules for imputation	Model/method for the main analytical methods	
					and the missing data will be subject to the imputation rules of the main estimator, that is, the multiple imputation method (MI) will be used to impute the missing data in the placebo group, and the J2R (jump to reference) method will be used to impute the missing data in the test group.
Estimand of key secondary endpoints	
The differences in the following measures in patients aged 12 years and older with moderate to severe AD and weighing ≥ 40 kg between the CBP-201 300mg Q2W group and the placebo group:
 
 • The proportion of subjects achieving EASI-75 at W16 • The proportion of subjects whose weekly average PP-NRS is decreased by ≥ 4 points from baseline at W16; • The proportion of subjects whose weekly average PP-NRS is decreased by ≥ 3 points from baseline at W16; 	FAS1 (will include all subjects in RS1 who have received the study drug at least once).	
For subjects who experience intercurrent events, their visits after the intercurrent events will be handled in accordance with the strategies for managing intercurrent events listed in Table 7.4.2.
 
If the target variable is still missing after application of the strategies for managing intercurrent events, the multiple imputation (MI) method will be used to impute the missing data in the placebo group, and the J2R (jump to reference)
	
For categorical variables, differences in response rates between the treatment group and placebo group and their 95% confidence intervals will be analyzed using the Cochran-Mantel-Haenszel test stratified by baseline disease severity (IGA 3 or 4).
 
For continuous variables, analysis will be performed using an MMRM model that will include treatment group, baseline disease severity (IGA 3 or 4), baseline value of the
	
Sensitivity analysis 1: When the target variable is still missing after application of the strategy for managing intercurrent events, categorical variables will be classified as treatment failure. Continuous variables should be imputed with WOCF.
 
Sensitivity analysis 2: For the subjects who are incorrectly stratified and randomized, the analysis will be performed using the stratification during randomization and the method the same as the main estimator;
 
Supplementary analysis 1: The analysis will be performed using the same method as the main estimand based on the PPS1.
 
Supplementary analysis 2: The treatment policy strategy will be used for all intercurrent events; the FAS1 will be used,

Label of estimand	Description of estimand	Main estimator			Sensitivity/ Supplementary analysis
		Analysis sets	Rules for imputation	Model/method for the main analytical methods	
	
 Change and percentage change in the weekly average PP-NRS from baseline at W16; The proportion of subjects achieving EASI-90 at W16 
A patient should be regarded as treatment failure if he/she uses prohibited drugs/treatments specified in the protocol for which the study treatment must be early terminated or other rescue therapy that has a major impact on the assessment of the key secondary endpoints due to poor response, or has premature discontinuation of treatment/EOT due to AEs. In this case, continuous variables should be imputed with WOCF.
		method will be used to impute the missing data in the CBP- 201 group.	corresponding endpoint, visit, interaction of visit and treatment group, and the LSMEAN estimate values and their 95% confidence intervals will be summarized.	and the missing data will be subject to the imputation rules of the main estimator, that is, the multiple imputation method (MI) will be used to impute the missing data in the placebo group, and the J2R (jump to reference) method will be used to impute the missing data in the test group.

In the J2R (jump to reference) method, when the data of subjects of the active treatment group are missing, it is assumed that their statistical results are the same as those of the placebo group, that is, it is considered that the pharmacological action of the drug for the active treatment group is the same as that of the placebo group. PROC MI will be used for J2R imputation, and the missing data of the active treatment group will be imputed with the results obtained by posterior predictive distribution of the placebo group. Markov Chain Monte Carlo (MCMC) will be used to extend the data, and a regression method will be used to generate M datasets (M is set as 30 for the primary analysis and as 1000 for other cases in this study). The imputed variables should include: treatment group, stratification factor (severity of baseline disease), baseline value of corresponding endpoint and measurement at each visit. Random seed is the earliest date of the first dose to all subjects.

Table 5 Random Seeds of Multiple Imputation

Endpoints	Random Seeds
IGA	Minimum date of the first dose
EASI	Minimum date of the first dose + 1
PP-NRS	Minimum date of the first dose + 2
BSA	Minimum date of the first dose + 3
SCORAD	Minimum date of the first dose + 4
DLQI	Minimum date of the first dose + 5
POEM	Minimum date of the first dose + 6

Tipping point analysis: To evaluate the robustness of the primary efficacy endpoint analysis, tipping point analysis should be performed on the primary efficacy endpoint at W16. The tipping point method is binary, that is, the assumptions of missing values of the active treatment group and the placebo group are mutually independent. Assuming that the response rate of missing values of the two groups increases by 10% from 0 to 100%, the subjects with a missing response in the two groups at a certain percentage will be randomly assigned as responders and non-responders in a specified number of imputed datasets randomly generated by the binomial distribution. Then the same analysis method as that for the primary study endpoint will be used to obtain the comparison results between the two groups in each imputed dataset. Finally, Rubin's Rule will be used to pool these results. If there is a pair of assumed response rate that overturns the study conclusion, that is, p value is more than 0.05, the two assumed response rates will be the cut-off points.

Subgroup analysis will be performed on the primary efficacy endpoint (the proportion of subjects whose IGA score is 0-1 and decreased by ≥ 2 points from baseline at W16) and the key secondary efficacy endpoint (the proportion of subjects achieving EASI-75 at W16) by gender (male/female), severity of baseline disease (moderate [IGA = 3]/severe [IGA = 4]), history of allergic diseases or allergy history (yes/no), baseline EASI ($<$ baseline median EASI/ \geq baseline median EASI), baseline PP-NRS ($<$ baseline median PP-NRS/ \geq baseline median PP-NRS). The analytical method is the same as the primary analysis method for the

primary efficacy endpoint and the key secondary efficacy endpoint. The subjects with missing subgroup variables will not be included.

Sensitivity analysis will be performed on the primary efficacy endpoint (the proportion of subjects whose IGA score is 0-1 and decreased by ≥ 2 points from baseline at W16) and the key secondary efficacy endpoint (the proportion of subjects achieving EASI-75 at W16) using the stratification during randomization and the method the same as the main estimator.

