Supplementary analysis will include all subjects (including the 75 subjects newly enrolled). The same analysis method as that for the primary analysis and Stage 2 analysis will be used.

The following 6 analysis datasets will be included in the primary analysis.

Screening set 1

It will include all subjects who have signed the informed consent form.

Randomization set 1 (RS1)

RS1 will include all subjects who have been randomized at baseline (D1), regardless of whether they have received the study drug.

Full analysis set 1 (FAS1)

FAS1 will include all subjects who have been randomized and received at least one dose of the study drug. Subjects are analyzed within FAS1 according to treatment assigned.

Per protocol set 1 (PPS1)

PPS1 will include all subjects in FAS1 without any major protocol deviation that affects efficacy analysis. Major protocol deviations that affect efficacy analysis have been discussed and determined at the blinded data review meeting for the primary analysis of the study on September 19, 2022, and have been discussed and determined again at the blinded data review meeting for the final analysis of the study on October 18, 2023. Minutes of the data review meeting will be presented in an annex.

By far, protocol deviations that affect efficacy analysis of the 255 subjects in Stage 1 are due to the following causes:

1. Missing doses (I. Missing W12 and W14 doses; II. Missing 3 doses in Stage 1, equivalent to a compliance with study drug lower than 70%);
2. Missing key efficacy results at W16 (both IGA and EASI missing);
3. Key efficacy results at W16 out of window (both IGA and EASI out of window >10 days);
4. Incorrect stratified randomization (only Stage 1);
5. Violation of inclusion or exclusion criteria (topical corticosteroids are used before baseline; baseline disease severity fails to meet the requirements);
6. Prohibited drugs (non-rescue treatment) that may affect efficacy

Safety set 1 (SS1)

SS1 will include all randomized subjects who have received at least one dose of study drug. Subjects are analyzed within SS1 according to the treatment they actually received.

PK set 1 (PKS1)

PKS1 will include subjects who have received at least one dose of CBP-201 active drug and had at least 1 collected and analyzable PK sample.

The Stage 2 analysis will be defined as the following analysis populations.

Randomization set 2 (RS2)

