Intercurrent event 3 (use of other prohibited drugs/treatments specified in the protocol other than those in Intercurrent Event 1 due to poor response, with a major impact on the assessment of the primary endpoint)	
 Initiation of SIT, or dose up-regulation; TCS or TCI; Phototherapy (NBUVB, UVB, UVA1, PUVA), sunbed or any other LED therapies; Bleaching baths more than 2 times a week; Any drug for the treatment of AD (except mild emollients) that may interfere with the evaluation of efficacy results or affect the evaluation of AD severity. 
The cumulative duration of use of the above prohibited drugs/treatments due to poor response before the W16 visit is more than 7 days, or the end date is less than 4 weeks away from the W16 visit.
	Composite strategy	
This type of intercurrent event occurs because of poor response, should be treated as non-response.
 
If it is a continuous variable, the data after the occurrence of the intercurrent event should be imputed with WOCF.

Intercurrent event 4 (premature discontinuation of treatment/EOT due to AEs)	The subject experiences an AE or SAE that is considered by the investigator to be intolerable before the W16 visit, and is unsuitable for continuing the study treatment, resulting in premature discontinuation of treatment/EOT.	Composite strategy	
This type of intercurrent event occurs because of poor safety of treatment, should be treated as non-response.
 
If it is a continuous variable, the data after the occurrence of the intercurrent event should be imputed with WOCF.

Intercurrent event 5 (the subject's administration is missing due to the COVID-19 epidemic)	The administration at two consecutive visits (W12 and W14) immediately before the W16 visit is missing or the administration in the Stage 1 treatment period is missing for ≥ 3 times.	Hypothetical strategy	The observed values are not used, and the J2R (jump to reference) method is used for imputation.
Intercurrent event 6 (use of prohibited	The following prohibited drugs/treatments have been used before the W16 visit not because of the poor response:	Hypothetical strategy	The observed values are not used, and the J2R (jump to

Label	Intercurrent event	Strategy	Remarks

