drugs/treatments specified in the protocol not for poor response, with a major impact on the assessment of the primary endpoint)	
• Dupilumab or any anti-IL-4Rα or IL-13 antibodies;• Topical PDE-4 inhibitors or JAK inhibitors;• Systemic treatment with corticosteroids or other immunosuppressive and/or immunomodulatory agents, such as cyclosporine, mycophenolate mofetil, azathioprine, methotrexate, or oral JAK inhibitors;• Cell depletion agents (e.g., rituximab) or other biological agents;• Other investigational drugs (non CBP-201) or treatments. 
Or
 
The cumulative duration of use of the following prohibited drugs/treatments not due to the poor response before the W16 visit is more than 7 days, or the end date is less than 4 weeks away from the W16 visit:
 
• Initiation of SIT, or dose up-regulation;• TCS or TCI (topical drugs can be used for AD lesion areas only);• Phototherapy (NBUVB, UVB, UVA1, PUVA), sunbed or any other LED therapies;• Bleaching baths more than 2 times a week;• Any drug for the treatment of AD (topical drugs can be used for AD lesion areas only) that may interfere with the evaluation of efficacy results or affect the evaluation of AD severity.		reference) method is used for imputation.

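### As worded, the tipping-point grid holds fixed the W16 outcomes that were set aside under intercurrent events 5 and 6 and refilled by jump-to-reference

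*SAP*

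**What the plan says.** SAP 7.4.2 (later version) assigns a hypothetical strategy to intercurrent events 5 and 6. Event 5 is doses missed because of COVID-19: both W12 and W14, or at least three in Stage 1. Event 6 is use of prohibited treatments "specified in the protocol not for poor response, with a major impact on the assessment of the primary endpoint". The remark for both is the same: "The observed values are not used, and the J2R (jump to reference) method is used for imputation".

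SAP 7.4.3 then sets the order of work for the main estimator. The event strategies come first, and a second rule picks up the remainder: "If the target variable is still missing after application of the strategies for managing intercurrent events, the multiple imputation (MI) method will be used" in the placebo group, with J2R in the CBP-201 group.

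Sensitivity analyses 1 and 2 carry the same condition. The first reads: "When the target variable is still missing after application of the strategy for managing intercurrent events, it will be classified as treatment failure". The second reads: "When the target variable is still missing after application of the strategy for managing intercurrent events, tipping point analysis will be used for analysis". The tipping-point paragraph later in 7.4.3 gives the grid, "Assuming that the response rate of missing values of the two groups increases by 10% from 0 to 100" per cent, independently in each arm. It says that "the subjects with a missing response in the two groups at a certain percentage will be randomly assigned as responders and non-responders". It does not mention events 5 or 6.

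Protocol Table 12.4 and SAP version 1.0 use the same condition for both sensitivity analyses. Event 6 is not in the protocol; it was added in the SAP.

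**The concern.** SAP 7.4.3 presents the tipping-point analysis as the check on how robust the primary result is. Such a check should vary every outcome that the primary analysis supplies by assumption. A W16 response set aside under event 5 or 6 and replaced by a draw from the placebo-based distribution is such an outcome: nothing in the data can confirm what the subject would have shown without the event. As worded, these draws stay as they are while only the other missing values move across the grid.

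At stake is the tipping region that the study reports. If these subjects are not rare, the planned grid may show no overturning pair of response rates, or a smaller overturning region, where a grid over all imputed outcomes would show more.

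**Working it through.** **Reading the wording**

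1. In 7.4.2, discarding the value and filling it by J2R are given together as the handling of events 5 and 6.
2. In 7.4.3, that handling is applied before anything is tested for being still missing.
3. An outcome filled at step 1 is therefore not still missing at step 2, and does not meet the condition for sensitivity analysis 2.
4. Nothing in the tipping-point paragraph brings it back.

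**Other analyses of the same subjects.** Supplementary analysis 2 uses treatment policy for all events, so it uses their observed values where these exist. Supplementary analysis 1 uses PPS1. The SAP section 6 list of deviations behind PPS1 includes the event 5 dose thresholds and "Prohibited drugs (non-rescue treatment) that may affect efficacy", so it removes largely the same people. Neither analysis varies the response assumed for them under the main estimand.

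**Inputs** (SAP 3.2): 170 and 85 subjects, response 27% v 9%, two-sided 5%, dropout 15%.

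**Plan's own figure.** With 144 and 72 completers, the pooled response is 0.21.
- Null SE = √(0.21 × 0.79 × (1/144 + 1/72)) = 0.0588.
- Alternative SE = √(0.27 × 0.73/144 + 0.09 × 0.91/72) = 0.0501.
- Power = Φ((0.18 − 1.96 × 0.0588)/0.0501) = 0.902, which agrees with the stated 90%.

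**Illustration.** The counts for events 5 and 6 are not given, so the fraction f per arm is an assumption, taken as equal in both arms. The test is unstratified: z = (a − p)/√(q(1 − q)(1/170 + 1/85)), with a and p the CBP-201 and placebo response rates and q = (170a + 85p)/255.

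*Events 5 and 6 the only imputed values.* With J2R held fixed, a = 0.27(1 − f) + 0.09f and p = 0.09. At the extreme corner of a grid that includes them (CBP-201 0%, placebo 100%), a = 0.27(1 − f) and p = 0.09(1 − f) + f.

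| f per arm | J2R fixed: difference, p-value | Corner: difference, p-value |
|---|---|---|
| 2% | 17.6 points, 0.001 | 15.6 points, 0.004 |
| 5% | 17.1 points, 0.0014 | 12.1 points, 0.027 |
| 10% | 16.2 points, 0.0022 | 6.2 points, 0.26 |

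The corner crosses 0.05 at about f = 6.2%, roughly 11 CBP-201 and 5 placebo subjects.

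In counts, start from 46/170 v 8/85 (p = 0.0011) and move k placebo and 2k CBP-201 subjects from a 9% response to the corner:
- k = 4: (46 − 0.72)/170 v (8 − 0.36 + 4)/85, p = 0.019.
- k = 6: (46 − 1.08)/170 v (8 − 0.54 + 6)/85, p = 0.058.

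*Other values also missing.* Assume 4% ordinary missing plus 3% events 5 and 6 in each arm.
- Planned corner (only the 4% varied): a = 0.27 × 0.93 + 0.09 × 0.03 = 0.2538; p = 0.09 × 0.93 + 0.09 × 0.03 + 0.04 = 0.1264; p-value 0.019.
- Widened corner (all 7% varied): a = 0.27 × 0.93 = 0.2511; p = 0.09 × 0.93 + 0.07 = 0.1537; p-value 0.076.

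Here the planned grid shows no tipping pair and the widened grid does.

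**Sensitivity analysis 1, for comparison.** With k = 6, setting these subjects to failure gives 44.92/170 v 7.46/85: a difference of 17.6 points, p = 0.0010. The starting values were 17.6 points and p = 0.0011.

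**The case against.** **The wording may already include these subjects.** The strategy column in 7.4.2 says only that the strategy is hypothetical; J2R stands in the remarks. If applying the strategy means only that the observed value is dropped, the outcome is then missing and enters the grid, and the tipping-point paragraph speaks simply of missing responses. This is a possible reading, but the remark gives discarding and imputing as one instruction. Two programmers could produce different tipping regions from the same text, which is itself a reason to settle it.

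**The subjects are already examined.** Comparing the J2R, observed-value and PPS1 results shows a good deal about whether the conclusion depends on them. That stands. What is missing is only the stress test of the imputed response. PPS1 also drops subjects for other reasons, so a change there could not be traced to events 5 and 6 alone.

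**The illustration is a worst case.** This also stands. With k = 6, CBP-201 at 0% and placebo at 50% gives p = 0.010, so nothing tips there. If 7.5% per arm were ordinarily missing, half the planned dropout, the planned corner would already give p = 0.096 and show a tipping pair without these subjects. The PPS1 list gives no counts, and its missed-dose item is not limited to COVID-19.

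**A reader might infer that sensitivity analysis 1 has the same fault and should also count these subjects as failures.** The documents do not support that. The SAP defines analysis 1 for the remaining missing values and does not present it as non-response imputation for everyone. Treating hypothetical-strategy events as failure would in effect apply the composite strategy that 7.4.2 keeps for poor response or poor safety. With equal fractions per arm it also leaves the difference unchanged.

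**Conclusion.** The gap is real but narrow. As worded, the tipping-point analysis leaves out W16 outcomes that were set aside under events 5 and 6 and refilled by J2R, and no other planned analysis varies the response imputed for them.

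Its size cannot be settled from the documents. Under the design rates, equal fractions per arm and an unstratified test, the extreme corner loses significance at about 6% per arm if these are the only imputed values. It does so at a lower fraction if other values are also missing.

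A reader might infer that the primary result is biased or that the trial's conclusion is fragile. Neither follows. The primary estimator is not in error, J2R is already unfavourable to CBP-201, and the calculations are extreme corners at assumed counts. This is a minor, cheap improvement to a robustness check.

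**What to change.** Reword sensitivity analysis 2 and the tipping-point paragraph in SAP 7.4.3 so that the 0–100% grid applies to every W16 outcome that is missing or was set aside under intercurrent event 5 or 6. Report the number of such subjects per arm, separately from those otherwise missing. Leave sensitivity analysis 1 unchanged.

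The cost is about a sentence of text and a change to the flag that selects subjects for the grid. If the analysis has already been run, a supplementary run with the wider flag is enough. The price is that the reported tipping region may look less favourable.
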